3.2.3. Exclusion Criteria

A subject will be excluded from the study if any of the following criteria are met:

1. Unstable patients
2. Multiple trauma patients
3. Patients with any allergies to ketorolac or any of the components in the nasal spray preparation
4. Patients with active peptic ulcer disease
5. Patients with a history of asthma, urticaria, or other allergic-type reactions after taking aspirin or other NSAIDS
6. Patients about to undergo major surgery
7. Patients with renal disease or at risk for renal failure due to volume depletion
8. Pregnant or nursing mothers
9. Patients with suspected or confirmed cerebrovascular bleeding, patients with hemorrhagic diathesis, incomplete hemostatis, and those at high-risk of bleeding
10. Patient with a nasal abnormality or illness that could affect the absorption of intranasal medication (such as: nasal discharge, rhinitis, acute upper respiratory infection, acute epistaxis, nasal polyp, nasal tumor)
11. Patient with any other contraindication to the use of Sprix, or in whom use of Sprix would not be consistent with the approved package insert

3.3 Rationale for Choice of Study Design and Population

This is a prospective efficacy, safety and tolerability trial in non-geriatric adults. Active treatment (a single dose of intranasal ketorolac) will be used. The population selected for this study, adult nongeriatric patients is a patient population that may benefit from the use of intranasal ketorolac. This is a population in whom intranasal ketorolac has been approved for use and in whom intranasal ketorolac has been shown to be safe and effective when used for other types of pain, specifically post-operative pain from major surgery and post-operative dental surgery. This is also a population in whom, other routes of administration of ketorolac, (e.g. intravenous, intramuscular and oral) have been shown to be efficacious and safe. Therefore, it seems highly likely that the intranasal form of ketorolac, in an appropriate dose of 30 mg will also be effective, safe and well tolerated.

4. STUDY TREATMENTS

4.1 Medication(s) for study treatment.

The following study treatments will be administered in this study:
Ketorolac Tromethamine (Sprix) Nasal Spray
Manufactured by Luitpold Pharmaceuticals

Subjects in the emergency department with acute pain will be administered a single dose of intranasal ketorolac as per standard application (see 4.2).

4.2 Method for Application of Ketorolac (Sprix) for the Treatment of Acute Pain

After identifying appropriate adult patients (see section 3.2), obtaining written consent (see section 9.3), and performing all pre-dose (baseline) pain assessments, ketorolac (Sprix) will be administered in the standard fashion.

A single dose of 31.5 mg will be administered with one 15.75 mg spray (in a metered dose of 100 µL per spray) in each nostril for a total of two intranasal sprays per patient that total 31.5 mg in 200 µL. Note: The time at which the second intranasal spray administration is completed is time 0. As stated above, the baseline pain assessments will be completed prior to the administration of the intranasal ketorolac (sprix).

4.3 Storage, Handling, and Administration

Current ICH GCP Guidelines requires the study investigator to ensure that study treatment (e.g. nasal spray bottles of sprix) deliveries from the Sponsor are received by a responsible person (e.g. research designee or pharmacist), and also ensure:

- The deliveries are recorded.
- The study treatment is handled and stored safely and properly.
- The study treatment is only dispensed to study subjects in accordance with the protocol.

The study treatment, intranasal ketorolac (sprix), will be stored in accordance to product labeling. Exposure to light, freezing and extreme heat should be avoided. It is recommended that the study treatments (e.g. unopened sprix) be stored between 36° F and 46°F (2°C and 8°C). During use, containers of Sprix Nasal Spray will be kept at controlled room temperature between 59°F and 86°F (15°C and 30°C), and out of direct sunlight. In this study, once a subject has received the intranasal ketorolac (sprix) spray, the bottle will be discarded. Each subject will receive the recommended dose of sprix (31.5 mg with one 15.75 mg spray in a metered dose of 100 µL per spray in each nostril for a total of two intranasal sprays [total of 200 µL] per patient from a new previously unused intranasal bottle of sprix. There will be only one use per bottle of sprix or one bottle of sprix per subject and there will be no other uses from the same intranasal spray bottle. Each patient will receive a single dose of intranasal ketorolac.

The study treatment (e.g. intranasal ketorolac or sprix) will be checked for expiration dates prior to use to ensure that expired product will not be used.

Study treatment inventory and accountability records will be kept by the study investigator or designee. Accountability will be documented throughout the study. The procedures below are mandatory:

The Investigator will not supply any study treatment to subject's not enrolled ion the study.

The research designee or pharmacist will store the study treatment (e.g. intranasal ketorolac: sprix) in a secure storage facility under controlled storage conditions, accessible only to persons authorized by the Investigator to dispense study treatment.

The research designee or pharmacist will maintain study inventory. The inventory will include a detailed accounting of materials received and dispensed to each subject.

At the conclusion of the study, a final study treatment inventory on the Treatment Accountability Log will be conducted and the results of this inventory will be recorded. It must be possible to reconcile delivery records with those of used and unused study treatment.

4.4 Packaging and Labeling

Intranasal ketorlac (sprix) is packaged in a nasal spray bottle that delivers a mist containing 15.75 mg in a metered dose of 100 μ L per spray administered in each nostril for a total of two intranasal sprays per patient with 31.5 mg total drug administered per dose.

4.5 Study Treatment Accountability

The study investigator/designee will verify that study treatments are received intact and in the correct amounts. This verification will be documented by signing and dating the Treatment Accountability Log. An accurate running inventory of the study treatment will be kept by the Investigator /designee, and will include the type of study treatment and the date the study treatment was dispensed.

4.6 Treatment Compliance

The prescribing information for each study treatment of intranasal ketorolac (sprix) and any other treatments (including medication(s), dose(s), route, and time(s) administered) by any route of administration (intravenous, intramuscular, oral, etc.) ordered by the clinician, (such as: other pain medications, sedatives, etc.) will be recorded.

5. SCHEDULE AND DESCRIPTION OF STUDY PROCEDURES

Study procedures will be performed as outlined in Figure 1 and summarized in Part 3: Investigational Plan.

Signed informed consent must be obtained from the subject before any study-related procedures may be performed.

Details regarding the informed consent process are provided in Section 9.3.

5.1 Study Procedures

5.1.1 Pre-Study Period

5.1.1.1 Present to the Clinical Site

Adult (non-geriatric) subjects ages 18 to 64 years with an acute painful injury or illness (such as an acute isolated musculoskeletal injury or a kidney stone) being seen in the emergency department may be eligible for this study.

5.1.2 Informed Consent

The patient will be approached to determine his/her interest in this study. If a subject is interested in the study, written informed consent is obtained (section 9.3) and screening will begin.

5.1.3. Patient Screening and Subject Log

After the patient presents to the clinical site, the Investigator/designee may review the patient's charts. A unique screening number will be assigned to patients that have had their records reviewed. This screening number will be assigned according to the institution's policies and procedures and may not contain any information that may assist in identifying the patient. A Subject Log will be maintained by the research site.

5.1.3.1 Screening Assessments

The following screening assessments will be completed during screening and the findings will be recorded.

- Inclusion and exclusion criteria (Sections 3.2.2 and 3.2.3, respectively)
- Patient number assigned
- Demographic information

5.1.4 Study Treatment

Study treatment assessments will be performed during the time the patient is in the clinical site and will be performed, if indicated at specific times (see subsections below) The following information will be obtained and the findings will be recorded:

Study treatment assessments at specified times (baseline prior to administration and after administration of intranasal ketorolac [sprix]) including vital signs (baseline, before administration of intranasal ketorolac) and after administration of intranasal ketorolac (prior to the patient leaving the clinical site, e.g. emergency department).

- Pain assessments
- Patient/health care provider questionnaires will be done prior to the patient leaving the clinical site
- Any side effects/adverse events
- Vital signs

5.1.4.1 Site Assessment

Pre/Post Administration of Intranasal Ketorolac (Sprix): The Healthcare provider will examine the patient's nasal mucosa and document the findings (such as: redness, drainage) both before administration and after administration of the intranasal ketorolac (sprix). Note: Any subject with abnormalities of the nasal passageway such as purulent discharge or epistaxis will be excluded from participation in the study.

5.1.4.2 Study Pain Assessments

Study pain assessments will be done before and after the administration of the single dose of intranasal ketorolac (sprix). All patients will have a minimum of two pain scores (NRS): a baseline (pre administration of the intranasal ketorolac) and a post administration of intranasal ketorolac. The time that the pain score is done, whether at baseline or post intranasal administration of the ketorolac, will be recorded any time a baseline or post-treatment NRS pain score is done. A post-treatment NRS pain score will be done immediately prior to the patient leaving the ED and immediately prior to the patient receiving rescue medication (e.g. any additional pain medication or sedatives) with the time post-treatment to be recorded. Depending on the length of time the patient is in the ED, additional NRS pain scores will be done, if possible. While the patient is in the ED, additional NRS pain scores will be recorded at specified times after study drug administration; specifically, at 20 minutes, 40 minutes, 1 hour, 2 hours, 3 hours, 4 hours, 5 hours and 6 hours for as long as the patient remains in the clinical site, in addition to time 0 (baseline = before administration of the study drug). (See Appendix 1) The pain scores will be compared and analyzed for statistical significance comparing the baseline (pre-study drug administration) with the "post-study drug administration or "treatment" pain scores.

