8. TERMINATION OF THE STUDY

9. ADMINISTRATION AND REGULATORY CONSIDERATIONS

9.1 Prior to Initiation of the Study.....
9.2 Institutional Review Board.....
9.3 Informed Consent/Authorization.....
9.4 Duties of the Investigator.....
9.5 Monitoring.....
9.6 Study Records.....
9.7 Records Retention.....
9.8 Subject Privacy/Authorization.....

BRIEF ABSTRACT

INTRODUCTION: Pain is a common reason for individuals to seek health care, especially emergency care. Ketorolac has numerous advantages over other pain medications, especially the opioids. The intranasal administration of ketorolac has been shown to be safe and effective in the treatment of postoperative pain following major abdominal surgery and post dental surgery, but there have been no studies evaluating the use of intranasal ketorolac for the treatment of acute pain in the emergency department.

METHOD: Twenty-five adults who are in the ED for an acute episode of pain will receive a single dose of intranasal ketorolac. Their pain before and after receiving the ketorolac will be measured by pain scales e.g. the numeric rating scale (NRS). The efficacy will be assessed by several measures including pain relief, pain intensity difference, global pain evaluation, global assessment of analgesia, and the summed pain intensity difference (SPID). This will allow for assessment of meaningful pain relief and the time to pain relief. The safety will be assessed by documentation of adverse events, vital signs, and clinical assessment of the nasal mucosa before and after the intranasal administration of the drug. The efficacy, tolerability and safety will also be assessed by patient and health care provider questionnaires.

PRIMARY OBJECTIVES: To determine the efficacy of ketorolac in an acute care setting, the emergency department (ED).

SECONDARY OBJECTIVES: To determine the safety and tolerability of ketorolac in an acute care setting, the ED.

PATIENT POPULATION: Adults: 18- 64 years of age, previously healthy men and nonpregnant women, with acute pain (e.g. an acute orthopedic injury such as a fracture or a kidney stone) being seen in the emergency department.

INTERVENTION: Single dose of intranasal ketorolac

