5.1.4.4. Standard-of-Care Procedures: Pain Management

Patients may receive additional medications as part of their emergency department treatment including additional pain medications, such as opioids. Any additional medications administered will be recorded. The need for additional medications (including the drug administered, the dose, the time, and the route of administration) will

be recorded. The need for additional pain medications (or the lack of need for additional pain medications) may also be a secondary efficacy endpoint.

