5.1.6 Efficacy Assessments

5.1.6.1 Pain Assessments

Pain scores will be recorded and documented before administration of the intranasal ketorolac (sprix) for a baseline pain assessment and at specified intervals after the administration of intranasal ketorolac (sprix). Post-treatment pain scores will be recorded immediately prior to discharge from the ED and immediately prior to any rescue (e.g. pain or sedative) medication. Post treatment pain scores will be collected for as long as the patient is in the clinical site and will be at 20 minutes, 40 minutes, 1 hour and for 1 hour intervals post treatment up to 6 hours (e.g. at 1, 2, 3, 4, 5, and 6 hours) in addition to pain scores immediately prior to rescue medication and immediately prior to discharge from the ED. Pain assessments will be by the Numeric Rating Scale (NRS).where 0 = no pain and 100 = the worst pain imaginable. (See Appendix 1)

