7. DATA ANALYSIS AND STATISTICAL METHODOLOGY

7.1 Planned Sample Size

Since this is a prospective, efficacy and safety trial, the planned enrollment is for 25 patients who will receive a single dose of intranasal ketorolac. This sample size provides 80% power to demonstrate that the mean pain intensity to demonstrate that the mean pain intensity difference (PID), (where the PID = post-treatment NRS – baseline NRS) differs from zero when the effect size is 0.56. The effect size was calculated as the mean PID divided by the standard deviation.

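### Pain is scored before added drugs but not before drug-free pain care, so in injured patients relief from a splint or similar care can enter PID as ketorolac effect and cannot reliably be separated later

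*Combined protocol and SAP*

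**What the plan says.** The Brief Abstract (Patient Population) describes acute pain with the examples "e.g. an acute orthopedic injury such as a fracture or a kidney stone". Sections 3.2.1, 3.2.2 and 5.1.1.1 likewise name acute musculoskeletal injury and kidney stone. No mix of conditions is given.

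Two sections set the event-triggered pain scores. Section 5.1.4.2 asks for one before the patient leaves the ED and one "immediately prior to the patient receiving rescue medication (e.g. any additional pain medication or sedatives) with the time post-treatment to be recorded". Section 5.1.6.1 repeats this: "Post-treatment pain scores will be recorded immediately prior to discharge from the ED and immediately prior to any rescue (e.g. pain or sedative) medication". Scores are also scheduled at 20 minutes, 40 minutes, 1 hour and then hourly to 6 hours while the patient stays. Section 5.1.4.2 requires the time of every score to be recorded, and qualifies the additional scores as being done where possible.

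Three sections cover what is recorded about other care:

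- Section 5.1.4.4 has a heading about standard-of-care procedures, but its text concerns drugs: "Any additional medications administered will be recorded".
- Section 5.1.5.3 (Medications during the Study) lists drug name, dose, route and time.
- Section 4.6 refers more broadly to other treatments ordered by the clinician, but details them by dose and route and gives drug classes as examples.

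Section 3.1 describes a nonblinded trial, and no comparator appears anywhere. Section 7.2 compares pain scores before and after treatment. It gives no rule for scores taken after rescue medication or after any other care.

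**The concern.** In a single-arm before-after comparison, nothing cancels the effect of a co-treatment given between the dose and the post-dose score. The pre-rescue score shows that the protocol recognises this for drugs, but it does not carry the idea over to drug-free care.

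Consider an injured patient dosed at time 0, splinted at 15 minutes and scored at 20, 40 and 60 minutes. The plan requires no score just before the splint, and no section clearly requires the splint's time. Whatever relief the splint gives is part of that patient's PID. Where such care relieves pain, the error favours efficacy, which is the primary objective.

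**Working it through.** **1. The plan's own figure.** Section 7.1 states that "the planned enrollment is for 25 patients who will receive a single dose of intranasal ketorolac", with 80% power to show that mean PID "differs from zero when the effect size is 0.56". The effect size is mean PID divided by its standard deviation (SD). A two-sided one-sample normal approximation gives Φ(0.56 × √25 − 1.96) = Φ(0.84) = 0.80, so the figure is reproduced. The t-test named in section 7.2 gives 76.6% at n = 25; that is a separate matter. Section 7.1 gives no separate mean or SD, so nothing there converts to NRS points. Below, relief is written as a positive number.

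**2. Does any section secure a score or a time for drug-free care?**

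| Section | Trigger or record | Covers drug-free care? |
|---|---|---|
| 5.1.4.2, 5.1.6.1 | Score before pain or sedative medication | No |
| 5.1.4.2, 5.1.6.1 | Scores at 20 min, 40 min, 1 h, hourly to 6 h; times recorded under 5.1.4.2 | Score times only, not the time of the care |
| 5.1.4.4, 5.1.5.3 | Medications given | No |
| 4.6 | Other treatments, described in drug terms | Unclear |

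**3. Possible size.** The documents give no share of patients, no amount of relief and no SD. All three are assumptions here.

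False contribution to mean PID = share of all patients × relief per patient:

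- low: 0.20 × 10 = 2 points
- middle: 0.30 × 20 = 6 points
- high: 0.50 × 30 = 15 points

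Smallest mean PID that is significant at n = 25 = t(0.975, 24)/√25 × SD = 2.064/5 × SD = 0.413 SD. This is 8.3 points if the SD is 20 and 10.3 points if it is 25. The middle case supplies 6/8.3 = 72% or 6/10.3 = 58% of that threshold, the low case at most 2/8.3 = 24%, and the high case exceeds it.

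**4. Chance of a positive result with no ketorolac effect.** This simulation uses n = 25, a two-sided t-test at 0.05 and relief in units of within-patient-group SD:

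| Share of patients | Relief (SD) | P(significant) |
|---|---|---|
| 20% | 0.5 | 7.5% |
| 20% | 1.0 | 14% |
| 40% | 1.0 | 41% |
| 50% | 1.0 | 57% |

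The nominal level is 5%. The result runs from almost harmless to serious, depending wholly on the assumed inputs.

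**5. Cost of cutting off scores at the first such care.** In the third-molar surgery trial summarised in section 1.2, time to perceptible relief was 21.5 minutes and to meaningful relief 66 minutes. A patient whose last usable score is at 15 minutes would show little drug effect even if the drug works. Suppose 20-50% of patients are cut off before onset, contribute a PID of zero, and the SD is unchanged. The planned effect then falls to 0.56 × 0.8 = 0.45 or 0.56 × 0.5 = 0.28, and two-sided t-test power falls from 77% to 58% or 27%.

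**The case against.** A reader might infer that relief from non-drug care can never be separated from the drug effect. The documents do not support that. Post-dose scores are scheduled and timed, so a splint at 50 minutes would have a 40-minute score before it. Section 4.6 can be read to cover non-drug treatments, and neither the case report form nor Figure 1 is available here. What remains is that the time of the care is not clearly secured, the additional scores are taken where possible, and the scheduled gaps are an hour long after the first hour. Separation is unreliable, not impossible.

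A reader might also take fracture reduction in general as the example. If a sedative or analgesic is given for it, the existing trigger applies. The gap concerns drug-free care, and only in the injury subset, whose share is unknown.

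It is tempting, too, to say that drug-free care should be analysed as rescue medication already is, using the last score before it. Sections 5.1.4.2 and 5.1.6.1 collect a pre-rescue score, but section 7.2 has no rule for using it, so there is nothing to extend. As the primary analysis, such a rule could replace a bias toward the drug with one against it, as step 5 shows.

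Finally, the size is entirely assumed. Care given before the baseline score would not enter PID, and a painful procedure could work against the drug. These objections limit the claim about size, but they do not close the recording gap.

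**Conclusion.** The point holds in limited form. If the plan is followed as written, relief from drug-free care given after dosing enters PID as ketorolac effect in injured patients, and the data may not allow it to be identified afterwards. Under the stated assumptions the inflation is 2-15 points of mean PID. The documents support neither end of that range over the other, and it assumes that all such care falls between dose and score and reduces pain.

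A reader might conclude that this bias by itself would make the trial positive. That follows only under the higher assumptions. The gap is worth closing because doing so is cheap and the time of the care may not be recoverable later. It is one part of the wider limitation of having no comparator.

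**What to change.** - **Sections 5.1.4.2 and 5.1.6.1:** add an NRS score immediately before any non-drug pain-relieving intervention (splinting, immobilisation, cooling, reduction without sedation or analgesia), without delaying care.
- **Case report form:** record the type and clock time of that intervention, and clarify section 4.6 so that it plainly includes it.
- **Section 7.2:** keep the planned PID analysis. Add a sensitivity analysis that uses only scores obtained before the first additional pain-relieving intervention, drug or non-drug, and report it beside the main result.

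The cost is one extra question and one form line in affected patients. The sensitivity estimate may be appreciably smaller, and biased against the drug, when the intervention comes before drug onset, so it should not replace the primary analysis. The change does not remove placebo response, regression to the mean or natural course.
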